3.4.1.3 Exploratory Efficacy Endpoints

The following will be used to explore the correlation of baseline programmed cell death-1 (PD-1) expression and other immune checkpoint molecules with outcome:

- Expression of programmed cell death-ligand 1 (PD-L1) and other immune checkpoint molecules in tumor
- Tumor-infiltrating lymphocyte (TIL) counts (e.g., CD3, CD4, CD8)
- EBV-associated genes/proteins (e.g., EBER, BZLF-1/ZTA, LMP-1, BGLF-4/PK, BXLF-1/TK, BRLF-1Rta)

In addition, the following potential biomarkers of activity will be evaluated for the combination therapy: histone H3 acetylation, plasma EBV DNA levels, ribonucleic acid (RNA) expression of selected immunological genes, and flow cytometry/IF/IHC for immune cell markers.

EBER, LMP-1, TIL counts, PD-L1, and other immune checkpoint molecules will be evaluated to identify potential resistance markers to therapy.

3.4.2 Safety Variables

Safety assessments consist of monitoring and recording all AEs, regular laboratory evaluation for hematology, blood chemistry, coagulation and urinalysis, periodic measurement of vital signs, ECGs, performance status, and physical examinations.

3.4.2.1 Adverse Events

An AE is any untoward medical event that occurs to a patient following the start of administration of the study drugs, whether or not considered study drug related. An AE can, therefore, be any unfavorable and unintended sign (e.g., an abnormal laboratory finding), symptom or disease temporally associated with the use of a drug, whether or not considered related to the drug. For example, it may be a new intercurrent illness, a worsening concomitant illness, an injury, or any concomitant impairment of the patient's health, including laboratory test values (as specified by the criteria below), regardless of etiology. Any worsening (i.e., any clinically significant adverse change in the frequency or intensity of a pre-existing condition) will be considered an AE. A diagnosis or syndrome will be recorded on the Adverse Events eCRF rather than the individual signs or symptoms of the diagnosis or syndrome.

An overdose, accidental or intentional, associated with an AE, or abuse, withdrawal, sensitivity, or toxicity to an investigational product should be reported as an AE. Overdoses with or without an associated AE will be recorded on the dosing eCRF. All patients will be monitored for AEs during the study and continue until 28 days after the last dose of study drugs or until a new anticancer treatment is started, whichever occurs.

Pre-existing conditions are not considered AEs unless the condition worsens by at least one grade following the start of administration of the study drugs.

3.4.2.2 Laboratory Parameters

Clinical laboratory evaluations will follow those outlined in the clinical study protocol and will be performed using a central or local laboratory. Evaluations include hematology, chemistry, urinalysis, coagulation, and pregnancy tests (for women of childbearing-potential only). Specific parameters to be collected are listed below:

- Hematology (blood): Complete blood count with differential to include white blood cells and differential, red blood cells, hemoglobin, hematocrit, platelets, mean corpuscular hemoglobin, mean corpuscular volume
- Chemistry (blood): Sodium, potassium, chloride, bicarbonate, blood urea nitrogen, creatinine, glucose, calcium, phosphate, magnesium, aspartate aminotransferase (AST), aminotransferase, alanine aminotransferase (ALT), total bilirubin, alkaline phosphatase, total protein, albumin, uric acid, lactate dehydrogenase (LDH), and serum amylase
- Coagulation (blood): prothrombin time, partial thromboplastin time, and international normalized ratio
- Urinalysis (urine): color (appearance), glucose, bilirubin, ketones, specific gravity, blood pH, protein, urobilinogen, nitrite, leukocyte esterase

3.4.2.3 Other Safety Variables

Electrocardiograms

Electrocardiograms will be performed as outlined in the clinical study protocol. Triplicate ECGs should be obtained in close succession from the first ECG to the third ECG. For each sampling time point, 3 standard resting 12-lead ECGs will be obtained in close succession and no more than 2 minutes apart (4 minutes total for 3 ECGs). Average corrected QT interval using Fridericia's method (QTcF) will be calculated to confirm eligibility.

When performed on days that include PK sample collection (Stage 1), two triplicate ECGs will be performed post-dose (within 1 hour of dose, separated by at least 15 minutes). Post-dose ECGs will be performed prior to and as close as possible to each PK sample collection at C_{max} (1 and 2 hours) and 4 hours.

For days with no scheduled PK sample collections, the ECG may be performed at any time during the clinic visit, or when clinically indicated, irrespective of the time of study drug dosing. All ECGs will be independently reviewed by a central laboratory.

Clinically significant abnormalities present at screening should be reported on the Medical History eCRF page. New or worsened clinically significant findings occurring after informed consent must be recorded on the Adverse Events eCRF page. All eligibility and patient management decisions should be based on the local reading of the ECG.

Vital Signs

Vital signs (temperature, blood pressure, and heart rate) will be obtained at the Screening visit (Day -28 to Day -1), on Day 1 of each cycle (Day 4 of Cycles 2 and 6), and at the End of Treatment (EOT) visit. Vital signs will be collected just prior to the first dose of valganciclovir and nanatinostat, and in concert and just prior to PK blood draws. On other indicated visit days, collect vital signs once (prior to dosing of study drugs, if administered in clinic).

Height and weight will be measured at screening (Day -28 to Day -1), and weight will subsequently be measured on Day 1 of each cycle (Day 4 of Cycles 2 and 6) and at the EOT visit. Height should additionally be measured in patients 12 to 17 years of age on Day 1 of each cycle (Day 4 of Cycles 2 and 6).

Physical Examinations and Performance Scales

Physical examinations will be performed at the screening visit only; symptom-directed physical examinations will be conducted at each visit through Safety Follow-up as outlined in the clinical study protocol. Performance status will be measured by ECOG performance status assessments and will be regularly evaluated as outlined in the clinical study protocol.

3.4.3 Pharmacokinetic Variables

Pharmacokinetic endpoints include observed plasma concentrations and estimated PK parameters for nanatinostat and ganciclovir, and these will be described in a separate analysis plan.

3.5 Data Quality Assurance

Report summaries will be generated using validated Base SAS® software, version 9.4 or higher, on a PC or server-based platform. Additional validated software may be used to generate analyses, as needed.

All SAS programs that create outputs or supporting analysis datasets will be validated by a second statistical programmer or biostatistician. At a minimum, validation of programs will consist of a review of the program log, review of output or dataset format and structure, and independent confirmatory programming to verify output results or dataset content. Additionally, all outputs will undergo a review by a senior level team member before finalization.

The content of the source data will be reviewed on an ongoing basis by project statistical programmers and statisticians. Data will be checked for missing values, invalid records, and extreme outliers through defensive programming applications, analysis-based edit checks, and other programmatic testing procedures. All findings will be forwarded to the project data manager for appropriate action and resolution.

4. STATISTICAL METHODS

4.1 General Methodology

Data will be analyzed by Emanate biostatistics personnel. Statistical analyses will be reported in the form of tables, figures, and listings, presented in rich text format, and using recommended ICH numbering. Output specifications for all tables, figures, and listings will be in conformance with guidelines specified by the ICH in Appendix 7 of the *Electronic Common Technical Document Specification (Apr 2003)*.

4.1.1 Reporting Conventions

The Simon 2-stage and post-Stage 2 expansion parts of the study will be analyzed separately. For safety analyses only, all patients who receive combination therapy over the course of the study will also be analyzed separately.

Tables and figures will be summarized by cohort within each part. A more detailed description for how these data will be presented for each type of analysis (e.g., safety, efficacy, etc.) is provided in subsequent sections herein. In general, all data collected and any derived data will be presented in patient data listings for all enrolled patients. Listings will be ordered by phase, site, cohort, patient number, and assessment or event date. The cohort presented in listings will be based on the planned assignment, unless otherwise noted.

In general, continuous variables will be summarized to indicate the study population sample size (N), number of patients with available data (n), mean, SD, median, first (Q1) and third (Q3) quartiles, minimum, and maximum values. Categorical variables will be summarized by the population size (N), number of patients with available data (n), number of patients in each category, and the percentage of patients in each category. Unless otherwise noted, the denominator to determine the percentage of patients in each category will be based on the number of patients with available data. Select ordinal data may be summarized using both descriptive statistics and counts and percentages of patients in each category, as appropriate.

Non-zero percentages will be rounded to one decimal place. Rounding conventions for presentation of summary statistics will be based on the precision of the variable of summarization, as it is collected in its rawest form (i.e., on the electronic case report form [eCRF] or as provided within an external file) and are outlined as follows:

- The mean and median will be rounded to one more decimal place than the precision of the variable of summarization;
- Measures of variability (e.g., SD, SE) will be rounded to two more decimal places than the precision of the variable of summarization; and
- Minimum and maximum values will be presented using the same precision as the variable of summarization.

Other statistics (e.g., CIs) will be presented using the same general rules outlined above or assessed for the most appropriate presentation based on the underlying data.

No formal statistical analysis will be performed to compare cohorts. No formal type-1 error adjustment will be performed at the interim analysis or at the final analysis. Descriptive statistics will be tabulated by cohort and reviewed to evaluate all study endpoints.

4.1.2 Summarization by Visit

Data summarized by study visit will be based on the nominal, scheduled visit label as reported on the eCRF. Data collected for the last patient visit will be summarized separately and this summary will be labeled as "End of Treatment" in the analysis.

Data collected at unscheduled visits will not be included in by-visit summaries but will be considered when endpoint derivations potentially include multiple visits (e.g., determination of baseline value, determination of worst post-baseline value, etc.). All data will be included in patient listings.

4.1.3 Data Handling Rules

Unless otherwise noted, values reported as greater than or less than some quantifiable limit (e.g., "<1.0") will be summarized with the sign suppressed in summary tables and figures, using the numeric value reported. Data will display patient listings to include the sign.

4.1.4 Baseline Value

Unless otherwise noted, the baseline value will be defined as the last value reported prior to the first dose of study drug.

4.1.5 Standard Calculations

Where appropriate, the calculated study day of each assessment or event will be presented with the assessment or event date on patient data listings, where study day will be determined as:

- The assessment/event date minus the date of first dose of study drug, if the assessment/event date is prior to the date of first dose; and
- The assessment/event date minus the date of first dose of study drug, plus one, if the assessment/event date is on or after the date of first dose.

Other variables requiring calculations will be derived using the following formulas:

- **Days:** A duration between two dates expressed in days will be calculated using the following conventions:
 - Later date earlier date + 1, if the earlier date is on or after the reference date of interest (e.g., date of first dose of study drug); or
 - Later date earlier date, if the earlier date is prior to the reference date of interest.

- **Months:** A duration expressed in months will be calculated by dividing the duration in days by (365.25 / 12).
- Years: A duration expressed in years will be calculated by dividing the duration in days by 365.25.
- **Change from Baseline:** Change from baseline will be calculated as the post baseline value minus the baseline value.
- **Percentage Change from Baseline:** Percentage change from baseline will be calculated as the change from baseline divided by the baseline value, multiplied by 100.
- **Second-Line EBV**⁺ **Lymphoma:** Relapsed or refractory disease following 1 prior systemic therapy (regimen). Inclusion in this subgroup will be determined using data collected for line of therapy on the Anti-Cancer Therapy Regimen eCRF.

4.2 Analysis Sets

The analysis sets are defined as follows:

- Intent-to-Treat Analysis Set: All patients who are enrolled into the trial, regardless of whether they received study treatment or not.
- Modified Intent-to-Treat Analysis Set: All enrolled patients who have received
 at least one dose of study medication with a confirmed diagnosis of lymphoma
 subtype by central pathology review. The primary efficacy analysis will be
 performed in the Modified Intent-to-Treat Analysis Set per FDA guidance and
 historical precedent.
- Efficacy-Evaluable Analysis Set: All enrolled patients who have received at least one dose of study medication, met all eligibility criteria, and have at least one adequate (radiographic) post-baseline tumor assessment.
- Safety Analysis Set: Patients who have received at least one dose of study medication will be summarized for safety by cohort and over all patients combined.

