3.4.1.2 Secondary Efficacy Endpoints

Secondary efficacy endpoints include the following:

- Complete response rate (CRR) defined as the proportion of patients who achieve a CR using the 2007 IWG NHL criteria (Cheson 2007) per IRC review, as well as per Investigator assessment.
- Time to response (TTR) defined as the interval from the start of study drug treatment to the date of first documented CR or PR per IWG criteria. TTR will be determined for response assessments per IRC review as well as by investigator.
- Duration of response (DOR) defined as the interval from the date of first documented CR or PR per IWG criteria to the date of disease progression, death due to any cause, or last adequate (radiographic) response assessment. Dates of disease progression and censoring will be determined as described in Section 4.5.6.2. Duration of response will be determined for response assessments per IRC review as well as by investigator.
- Duration of complete response (DOCR) defined as the interval from the date of first documented CR per IWG criteria to the date of disease progression, death due to any cause, or last adequate (radiographic) response assessment. Dates of disease progression and censoring will be determined as described in Section 4.5.6.2. Duration of complete response will be determined for response assessments per IRC review as well as by investigator.
- Time to next anti-lymphoma treatment (TTNLT) defined as the interval from the start of study drug treatment to the date of next anti-lymphoma treatment (including chemotherapy, radiotherapy, radioimmunotherapy, or immunotherapy). Patients who do not receive subsequent anti-lymphoma treatment will be censored at the date of their last non-missing disease assessment prior to the start of therapy.
- Progression-free survival (PFS) defined as the interval from the start of study drug treatment to the date of first documented disease progression, initiation of new antineoplastic therapy, or death from any cause, whichever occurs first. Dates of disease progression and censoring will be determined as described in Section 4.5.6.2.
- Time to progression (TTP) defined as the interval from the start of study drug treatment to the date of disease progression. Patients whose disease does not progress will be censored at the date of their last tumor assessment.

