- Overall survival (OS) defined as the interval from the start of study drug treatment to the date of death, for any reason. Patients without documentation

of death at the time of analysis will be censored at the date the patient was last known to be alive.

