4.5.1 Datasets Analyzed

Efficacy summaries will be produced as described in Section 4.2. Efficacy summaries will be repeated for the Efficacy Evaluable Analysis Set as supportive evidence and to assess the robustness of efficacy findings. Efficacy summaries may also be repeated for the Intent-to-Treat Analysis Set if meaningfully different than the Modified Intent-to-Treat Analysis Set. A data listing of patients excluded from the Intent-to-Treat, Modified Intent-to-Treat, and Efficacy Evaluable Analysis Sets, to include the reason for exclusion, will be presented.

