4.5.6.2 Handling of Dropouts or Missing Data

Overall response is based on those patients with available data (baseline and post-baseline response assessment). Non-evaluable patients are considered non-responders and will be included in the denominator. Progression-free survival and DOR will be right-censored for patients who meet one of the following conditions: 1) non-protocol systemic anti-cancer treatment started before documentation of disease progression or death, 2) death or disease progression after more than one missed disease assessment visit, or 3) alive and does not have documentation of disease progression before a data analysis cutoff date. These conventions are based on the FDA Guidance for Industry, Clinical Trial Endpoints for the Approval of Cancer Drugs and Biologics (2018) and Clinical Trial Endpoints for the Approval of Non-Small Cell Lung Cancer Drugs and Biologics (2015). The analyses of PFS and DOR will be right-censored according to the conventions described in the table below.

Table 3 Censoring Conventions for Progression-Free Survival, Time to Progression, and Duration of Response

Situation	Date of Progression for Censoring	Outcome
No baseline tumor assessments	Randomization (if applicable) or enrollment	Censored
New anti-cancer therapy started before documentation of PD or death	Date of last disease assessment prior to start of new anti-cancer therapy	Censored*
Death or PD immediately after more than one consecutively missed disease assessment visit	Date of last disease assessment visit without documentation of PD that is before the first missed visit	Censored
Alive and without PD documentation	Date of last disease assessment	Censored
Death or PD between planned disease assessments	Date of death or first disease assessment showing PD, whichever occurs first	Progressed

Situation	Date of Progression for Censoring	Outcome
Death before first disease assessment	Date of death	Progressed

*PFS, TTP, DOR will additionally be analyzed without censoring for hematopoietic stem cell transplant

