4.5.6.6 Use of an "Efficacy Subset" of Patients

The primary efficacy analysis will be performed in the Modified Intent-to-Treat Analysis Set; the Intent-to-Treat and Efficacy Evaluable Analysis Sets will be utilized as sensitivity analyses.

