4.5.6.8 Examination of Subgroups

The primary efficacy endpoint may be summarized by various subgroups of interest based on baseline and demographic categories including age (<65 years of age and \ge 65 years of age), ECOG performance status at study entry (0, 1, and 2), number of prior systemic therapies (1 line and 2+ lines), stage of disease at study entry (Stages 1-2 and Stages 3-4), gender, and race. Summaries by subgroup will only be produced if there are at least 6 patients in the category of interest.

For the post-Stage 2 expansion part of the study, all efficacy analyses will also be summarized in the Modified Intent-to-Treat and Efficacy Evaluable Analysis Sets for the subgroup of patients with second-line EBV⁺ lymphoma as defined in Section 4.1.

Additional subgroup analyses may be performed post-hoc, as appropriate.

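### The supportive Efficacy-Evaluable set requires a post-baseline scan, yet OS, PFS, TTP and TTNLT are repeated in it as a robustness check, which tilts those results and the supportive ORR in the favourable direction

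*SAP*

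**What the plan says.** SAP 4.2 defines the EE set as enrolled patients who were dosed, met all eligibility criteria and have at least "one adequate (radiographic) post-baseline tumor assessment". SAP 3.1 puts the first scheduled assessment at Week 8 (Week 6 in Cohort 3a).

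SAP 4.5.1 states: "Efficacy summaries will be repeated for the Efficacy Evaluable Analysis Set as supportive evidence and to assess the robustness of efficacy findings". For the second-line subgroup in the expansion, SAP 4.5.6.8 goes further: "all efficacy analyses will also be summarized in the Modified Intent-to-Treat and Efficacy Evaluable Analysis Sets". Neither section exempts an endpoint or sets a landmark.

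The time-to-event endpoints start at first dose. SAP 3.4.1.2 has OS "defined as the interval from the start of study drug treatment to the date of death, for any reason" and "Progression-free survival (PFS) defined as the interval from the start of study drug treatment to the date of first documented disease progression" (or the other PFS events). TTP and TTNLT have the same origin.

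SAP 4.5.6.2 has two protections for early failures. Table 3 treats "Death before first disease assessment" as an event on the date of death, and non-evaluable patients count as non-responders in the response denominator.

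The primary analysis is in the mITT set, which needs a dose and centrally confirmed subtype but no post-baseline scan. SAP 4.5.6.6 adds that "the Intent-to-Treat and Efficacy Evaluable Analysis Sets will be utilized as sensitivity analyses". The ITT repeat, however, is conditional in SAP 4.5.1: "Efficacy summaries may also be repeated for the Intent-to-Treat Analysis Set if meaningfully different" from the mITT set.

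**The concern.** Membership of the EE set depends on something that happens after treatment starts, while the survival clock starts at first dose. Anyone who dies without an adequate post-baseline scan is excluded, so every EE patient is guaranteed to be alive up to the first scan. That guaranteed interval is immortal time, and it is credited to the treatment.

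Both protections in SAP 4.5.6.2 stop working inside this set. The early-death row of Table 3 can contain nobody, and patients with no scan are deleted rather than counted as non-responders.

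At stake is the meaning of the robustness check. If the EE result matches or improves on the mITT result, a reader will take that as reassurance, but a set that removes some of the worst outcomes cannot provide it. The EE repeat is also the only one the SAP commits to without condition. The ITT repeat, which would work against this optimism, is optional.

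**Working it through.** **Inputs**
- First scheduled scan: Week 8 = 56 / (365.25/12) = 1.84 months (SAP 3.1; month length from SAP 4.1.5).
- Historical median OS in relapsed or refractory PTCL: 6.5 months (Protocol 1.1.2).
- Share of treated patients without a post-baseline scan: not given. Assumed 5% or 10%, with an upper value derived below.

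**The plan's own figure.** The documents give no figure for the size of the EE set or its effect. The nearest is the first row of SAP Table 4: 42.5% of 40 patients, 95% CI 27% to 59%. The exact Clopper-Pearson interval for 17/40 is 27.0% to 59.1%, so it reproduces.

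**Response rate.** An unscanned patient cannot be a radiographic responder. With unscanned share d, the numerator x is unchanged and the denominator shrinks:

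EE ORR = x / [n(1 − d)], so the factor is 1/(1 − d).

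| d | Factor | 17 responders, 40 treated |
|---|---|---|
| 0 | 1.00 | 17/40 = 42.5% (27.0% to 59.1%) |
| 5% | 1.05 | 17/38 = 44.7% (28.6% to 61.7%) |
| 10% | 1.11 | 17/36 = 47.2% (30.4% to 64.5%) |

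**Overall survival.** Suppose a share f of treated patients die before Week 8, all unscanned, and the hazard afterwards is h = ln 2 / 6.5 = 0.1066 per month.
- EE median from first dose = 1.84 + 6.5 = 8.34 months, whatever f is.
- All-treated median = 8.34 + ln(1 − f)/h.
- f = 5%: 8.34 − 0.48 = 7.86 months; 8.34/7.86 = 1.06.
- f = 10%: 8.34 − 0.99 = 7.35 months; 8.34/7.35 = 1.13.

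The comparator here is the all-treated median under the same scenario (7.86 or 7.35), not 6.5. With only 5% or 10% dead by Week 8, the overall median is no longer 6.5.

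**Upper value.** If survival were exponential from first dose with median 6.5 months, the share dead by Week 8 would be 1 − 2^(−1.84/6.5) = 17.8%. If none of them had been scanned, median OS would read 8.3 instead of 6.5 months, 12-month OS 33.8% instead of 27.8%, and the ORR factor would be 1/(1 − 0.178) = 1.22.

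**Which endpoints.** For OS and PFS the bias comes through unscanned deaths. For TTNLT it comes through patients who stop unscanned and soon start other treatment. For TTP it depends on whether Table 3's early-death row is applied: the table title includes TTP, but the TTP definition in SAP 3.4.1.2 does not count death. DOR and duration of complete response are not affected by the scan condition, because every responder has a scan. The separate eligibility condition can move ORR either way and is not part of this point.

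**The case against.** The other side has a good deal right.

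- **A reader might infer that the trial's ORR and survival results are biased upward.** The documents do not support that. The primary analysis is in mITT, with non-evaluable patients kept as non-responders; results are described as descriptive; and no stated decision rule uses the EE set.
- **A reader might infer that the EE set is the only sensitivity analysis.** SAP 4.5.6.6 names ITT too. What stands is that SAP 4.5.1 makes the ITT repeat optional.
- **A reader might infer that everyone who deteriorates before Week 8 is lost.** Protocol 7.3.1.2 requires suspected progression to be confirmed by imaging as soon as possible, and an end-of-treatment scan unless one was done in the previous 4 weeks. Patients so imaged stay in the EE set as progressors. Only those never adequately scanned leave.
- **A reader might take 18%, or larger shares from the shorter historical medians for other subtypes, as the expected loss.** These are upper values. They assume exponential survival and no scans among early deaths, and they come from other populations, while this trial requires life expectancy above 3 months.
- **Transparency.** SAP 4.5.1 already plans a listing of patients excluded from the EE set with reasons, so a reader could recompute ORR by hand.
- **Scope of the wording.** An unqualified reference to all efficacy analyses appears only in SAP 4.5.6.8, for the second-line subgroup, and Protocol 9.6.1 has OS include all enrolled patients. But SAP 1 says the SAP supersedes the protocol's analysis plan, OS and PFS are listed there as efficacy endpoints, and nothing removes them from the general repeat in SAP 4.5.1.

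These points limit reach and size. They do not make a scan-conditioned survival curve a valid robustness check.

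**Conclusion.** The point holds for the supportive EE summaries only. As written, the SAP repeats endpoints timed from first dose in a set that requires a later scan. OS and PFS there are favourably biased whenever any treated patient dies unscanned, and the missing-scan exclusion can only raise EE ORR and CRR.

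The size depends on a share the documents do not give. At an assumed 5% or 10% dying unscanned by Week 8, and a 6.5-month-median hazard afterwards, ORR is multiplied by 1.05 or 1.11 and median OS rises by about 6% or 13%. The 18% scenario is a ceiling for that median, not an estimate. The change should be made because the bias has a known direction and removing it costs almost nothing; the primary conclusion does not depend on it.

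**What to change.** In SAP 4.5.1 and 4.5.6.8:
1. Limit the EE set to ORR and CRR summaries, labelled as conditional on having an adequate post-baseline scan.
2. Analyse OS, PFS, TTP and TTNLT only in the mITT and ITT sets.
3. Make the ITT repeat unconditional, including for the second-line subgroup. Because the ITT set may contain patients never dosed, state the time origin for them.

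Redefining EE membership so that early deaths or toxicity stops count as evaluable non-response is a possible further step, but a debatable one. It is not needed once the response summary carries the label in item 1.

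Cost: SAP wording and table changes, with no new data. The supportive results become slightly less favourable.
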